Our recruitment goals include: 50% women and 30% minority. We will recruit these individuals using community-based recruitment strategies, including newspaper and radio advertisements, e-mail, direct inclinic recruitment approach as well as, portal messages, and mass mailings. Specific inclusion/exclusion criteria (see table) are in place to eliminate those that may be adversely affected by the interventions or that are not able to comply with the interventions. To reduce adverse effects of dietary weight loss, we exclude individuals that are non-obese, those with recent weight loss, those who have osteoporosis, and/or anyone on medications that may affect bone density. To reduce fall risk, we set an upper age limit on recruitment of 85 years and will exclude anyone who cannot walk unassisted over a short distance or who has had >1 fall in the past year (see Table below).

Participant Screening and Randomization

All individuals who respond to our recruitment strategies will call a toll-free phone number and a recruiter will describe the study and perform a brief screen for general eligibility. They will be asked about their

Criteria	Inclusion	nclusion Exclusion					
Age	55-85 years		Self-report				
Obesity status	BMI=30-45 kg/m ²		Measured on scale				
Functional status		-Dependent on cane or walker to walk a short distance; >1 fall (injurious or non-injurious) in past year (does not include falls where participant was pushed/pulled by another object and was not injured) -Vision insufficient to read a smartphone screen, unable to read	Self-report				
Weight stability	Weight stable—no loss or gain (±5%) in past 6 months;		Self-report				
Physical activity status		-Participation in regular resistance training and/or > 20 mins on 2+ d/w of aerobic exercise in past 6 months -No contraindication to exercise	Self-report				
Cognitive status		Montreal Cognitive Assessment <22	Questionnaire				
Co- morbidity/health status		Uncontrolled hypertension (>160/90 mmHg);Current or recent past (within 1 year) severe symptomatic heart disease, uncontrolled angina, stroke, chronic respiratory disease requiring oxygen, neurological or hematological disease; cancer requiring treatment in past yr, except non-melanoma skin cancers	BP measurement Self-report on Medical History form				
Medication use		Regular use of: growth hormones, oral steroids, or prescription osteoporosis medications	Self-report and medication inventory				

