Research participation	Willing to provide informed consent; Agree to all study procedures and assessments; Able to provide own transportation to study visits; owns an Android or Apple smartphone.	Current participation in other research study targeting pain, physical activity, or weight loss	Self-report				
Pain Status	Pain in 2 or more of the following sites on most days for the previous 3 months: back, neck, shoulders, hips						

	and/or knees		
Surgery		Joint replacement or orthopedic	
		surgery within previous 6 months	
		or planning to have orthopedic	
		surgery in the next 6 months	

age, weight, height, current physical activity habits, body weight in the past year, medical history, current medications, and eligibility to participate. All participants must conform to the study's inclusion/exclusion criteria. All participants, with questions regarding medical history will be cleared by a study physician (AB) and then will be approved for participation by study PI

Those who pass phone screening will be scheduled for a 1:1 development session (Phase I) or screening-visit (Phase II) at a WFBMC-affiliated facility. The screening visit will allow participants to complete self-reported questionnaires and tests of physical function. During both phases, participants provide written informed consent and complete a HIPAA authorization form in accordance with our IRB policy prior to collection of any data. For both phases, the first visit begins with measurement of weight and height to calculate BMI. Individuals who meet the BMI criteria will undergo a medical history and a cognitive test (MoCA¹⁹). The medical history (including blood pressure) will exclude those not meeting inclusion criteria with regard to medication use, health status, or cognitive status. Eligible participants will be randomized to treatment using a web-based randomization scheme, stratified by sex with random block sizes.

Study Procedures

A timeline for phases I and II is provided below.

Phase I – Person-Centered Design and Development

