improvements made to the interface following each small grouping of interviews (n=1-3 interviews). Finally, after the interview session, the participant will bring all study peripherals to their home (i.e., Fitbit device, connected scale), and engage with the app for one week. During this period, the participant will also complete one burst of ecological momentary assessment. Following this one-week period, the participant will return to the research site to return equipment, complete the System Usability Scale ¹⁶, and receive remuneration for their time. This process is to be completed iteratively until the investigative team is confident that no further iterations are needed, and participants no longer provide meaningful interface critiques.

Phase II - MORPH Pilot Study

Whereas Phase I is concerned with ensuring the usability and desirability of the application for the target population, Phase II is meant to establish the efficacy of the program when delivered in the home. Accordingly, Phase II is a randomized controlled pilot study in which participants (N=30) will enter the study in up to three small waves. We will begin with a trial run of ~5 individuals who will all be assigned to the intervention condition to pilot all facets of the intervention. For the duration of each wave, intervention staff will keep detailed notation of software and usability challenges, and iterations will be made in between waves. Notably, these iterations will not affect the overarching structure of the intervention, but will ensure all components of the program are maximally usability for the older adult with chronic pain. The participants that are not randomized to active intervention after screening will receive monthly phone calls to keep them engaged in the study until they return for the follow up visit.

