- 12. Ecological Momentary Assessment: EMA will be used to study within-person and within-day interactions between sleep quality and duration (assessed via items from the Pittsburgh Sleep Quality Index²⁷), affect (assessed via the feelings scale), and level of pain.

During weeks 1, 5, and 9, participants will complete week-long daily assessments. Participants will be instructed to complete assessments upon waking up in the morning and immediately prior to going to bed at night. Additionally, each participant will receive up to five daily text message prompts with links to secure web-based questionnaires. Each assessment will take the average user less than one minute to complete, and will contain all items with the exception of sleep items, which will be assessed only during the first assessment of the day.

- 13. App Use: We will note how many times the app is opened from the home screen throughout the study.
- 14. Retention: We will record retention as the number of consented participants who complete baseline and follow-up testing.

Statistical Analyses

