For Specific Aim 1 (development of mHealth application), we will use simple descriptive statistics and qualitative data to evaluate usability and feasibility of the intervention. For Specific Aim 2 (pilot RCT), the goal of the analysis is to (1) estimate the effect size of the intervention such that the results can be used to power a future larger RCT, and (2) explore appropriate methods and models for analyzing EMA/EMI data. We plan to estimate the effect size using the following generalized linear model: $Y_{FU} = \beta_0 + \beta_1 Y_{BL} + \beta_2 Int + \text{covariates} + \varepsilon$, where Y represents the primary outcomes (SPPB score, PROMIS pain scales), subscripts FU and BL denote measurement at week 12 follow up and baseline respectively. Intrepresents intervention status, \Box represents regression coefficient, and ε represents random error. Because of the small sample size, we may include important covariates (e.g., gender, age) into the model if the two arms happen to be highly imbalanced. In case covariates are used, effect sizes will be estimated using the adjusted values from the above equation. We also plan to conduct similar analyses of secondary outcomes of the RCT (e.g., WL & sedentary behavior) using the aforementioned model and apply the appropriate model link function if the secondary outcome is not continuous. Although our primary goal is to determine feasibility and effect size using data collected from baseline and week 12, we do recognize the potential value of the intensively collected EMA data. Exploratory analyses, including visualization will be used to study the utility of EMA data, which include both pain and psychosocial variables. For example, we will determine if preliminary evidence supports the crosslagged reciprocal relationship between pain and self-efficacy. Another example is the examination of intra-person vs inter-person variation in the EMA variables. The exploratory analysis is expected to inform the analytic plan for a future larger study.

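### Randomisation is stratified by sex, but the outcome model includes sex only optionally, under an undefined imbalance condition that stratification makes very unlikely to be met at randomisation

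*Combined protocol and SAP*

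**What the plan says.** The Participant Screening and Randomization section describes allocation as "stratified by sex with random block sizes". Sex is the only stratification factor.

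The Statistical Analyses section regresses the week-12 value on the baseline value, intervention status and an open covariates term. The only rule for that term is "we may include important covariates (e.g., gender, age) into the model if the two arms happen to be highly imbalanced". If covariates do enter, "In case covariates are used, effect sizes will be estimated using the adjusted values from the above equation", so the reported effect size depends on the choice. Secondary outcomes use the same model, with permission to "apply the appropriate model link function if the secondary outcome is not continuous".

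No other section puts sex in the model, defines the degree of imbalance that counts, or says which variable's imbalance admits which covariate.

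**The concern.** The design rule and the analysis rule pull against each other. Stratified blocks are there to prevent sex imbalance, yet the plan considers adjusting for sex only if imbalance appears. Read strictly, at randomisation, the factor built into the design would almost never reach the model. Read loosely, the analyst decides after seeing the arms.

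Balancing sex by design removes its contribution from the true sampling variance of the treatment difference. A model without sex still counts that contribution as residual error. If sex predicts outcome given baseline, the reported standard error and residual variance are then too large and the test is conservative. The treatment difference is not biased and the false-positive rate is not raised.

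The first stated aim of the Aim 2 analysis is an effect size for powering a later trial. An inflated residual SD would affect that planning only if the effect size is standardised by the residual SD and the later model includes sex. The documents state neither.

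**Working it through.** The documents give no imbalance threshold, significance level, SD or sex effect, so there is no figure of the plan's own to reproduce. The check asks how often the condition could be met and what omitting sex costs.

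**Inputs from the documents.** N = 30 in two arms; stratification by sex; a recruitment goal of "50% women and 30% minority"; the model with baseline and intervention.

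**Assumptions.** 1:1 allocation (15 per arm), 15 women, block sizes 2/4/6, a continuous outcome, baseline correlation 0.5, no treatment effect, two-sided 5% level. Let r be the share of post-baseline outcome variance explained by sex. With half women, r = 2%, 5%, 10% and 20% correspond to a gap between men and women of 2√(r/(1−r)) = 0.29, 0.46, 0.67 and 1.0 residual SD.

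**1. How often could the condition be met for sex?** Chance that the arms differ in percentage of women by more than the stated number of points (20,000 simulated trials per row):

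| Situation | >10 | >20 | >30 |
|---|---|---|---|
| At randomisation, 15 women and 15 men | 1.7% | 0% | 0% |
| At randomisation, 21 women and 9 men | 2.9% | 0% | 0% |
| Each participant lost with probability 20% (assumed) | 33% | 7.0% | 1.0% |
| Exactly 6 of 30 lost (assumed) | 24% | 4.3% | 0.3% |
| 25 randomised plus 5 pooled run-in participants | 25% | 0.4% | 0% |
| The same, with 20% independent dropout | 40% | 10.6% | 2.0% |

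The run-in rows arise because the Phase II section says "We will begin with a trial run of ~5 individuals who will all be assigned to the intervention condition" without saying whether they are analysed. A separate simulation found a difference of 20 points or more at randomisation in at most 0.02% of stratified trials, against 19–34% without stratification.

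If age imbalance were read as also admitting sex, the arms would differ in mean age by more than 0.25 SD in 49% of trials and by more than 0.5 SD in 17% at randomisation.

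**2. What does omitting sex cost?** With sex exactly balanced, the residual mean square without sex is [27(1−r) + 30r]/27 on 27 degrees of freedom. With sex it is 1−r on 26. The ratio of confidence-interval widths is

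√{[27(1−r) + 30r] / [27(1−r)]} × t(27)/t(26), with t(27)/t(26) = 2.052/2.056 = 0.998.

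At r = 10%: (24.3 + 3)/24.3 = 1.123; √1.123 = 1.060; × 0.998 = 1.058.

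Width of the interval without sex relative to with sex (simulation, 9,000 trials per cell):

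| r | Closed form | Simulated, no dropout | Simulated, 20% dropout | Type I error without sex, no dropout |
|---|---|---|---|---|
| 0% | −0.2% | −0.3% | −1.0% | nominal within simulation error |
| 2% | +0.9% | +0.7% | 0% | 4.8% |
| 5% | +2.7% | +2.5% | +1.8% | 4.6% |
| 10% | +5.8% | +5.5% | +4.7% | 4.1% |
| 20% | +12.8% | +12.2% | +11.6% | 2.8% |

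The simulation SE of the type I error is about 0.2 points. At r = 10% without dropout, the true sampling SD is 0.306 without sex and 0.305 with it, but the mean reported SE is 0.321 and 0.304. Bias is −0.003 in both models, within simulation error. Residual variance is 12% larger without sex.

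**3. Does the conditional rule recover the loss?** Only partly. After 20% independent dropout, a rule of more than 10 points leaves the interval 3.5% (r = 10%) or 7.9% (r = 20%) wider than always including sex. A rule of more than 20 points leaves it 4.6% or 11.0% wider.

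**4. Later trial, under the two conditions named above.** At 0.5 residual SD, 80% power and two-sided 5%, n per arm = 2(1.960 + 0.842)²/0.5² = 62.8, so 63. Multiplying by 1−r gives 60, 57 or 51 with sex at r = 5%, 10% or 20%.

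**5. Scale of pilot noise.** The coefficient of variation of the residual-variance estimate is √(2/27) = 27%, more than twice the 12% inflation at r = 10%.

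**The case against.** A model without the stratification factor is still valid, and keeping the model small is defensible in a 30-person pilot aimed at estimation. The plan names gender as a candidate, and baseline is always included. That sex imbalance is rare at randomisation shows stratification working; the clause can be seen as a fallback for the analysed set. The harm depends on a sex effect that the documents do not supply, and the large figures need a gap of a full residual SD between men and women with the same baseline score. At r = 2% the loss is under 1%, and at zero, adding sex costs a little.

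Most of this stands and limits the weight of the point. Omission is an inefficiency and an open choice, not an error. Reading age imbalance as a route for sex is strained, because the imbalanced covariate is naturally the one added. A difference of 10 points is about 1.5 people per arm, hardly a marked imbalance.

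Two things remain. As a fallback the clause has no threshold, so it settles nothing, and it recovers only part of the lost precision. And whether sex belongs in the model follows from how participants were allocated, which is known before any data are seen.

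**Conclusion.** The point holds as a minor, optional improvement. The plan stratifies by sex but does not determine whether the analysis will reflect it, and the stated condition is very unlikely to be met for sex at randomisation (about 2% of trials at more than 10 points, none at more than 20).

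The consequence is a conservative standard error and test. The interval is 0.7% to 12.2% wider if sex explains 2% to 20% of post-baseline variance, and there is no loss if it explains none. These figures rest on 1:1 allocation, equal numbers of women and men, the assumed block sizes, a 5% level and a continuous outcome. The effect on a later sample size is conditional and should not be treated as a main consequence.

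**What to change.** In Statistical Analyses, replace the conditional covariate sentence with:

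> For the primary outcomes (SPPB, PROMIS pain intensity and PROMIS pain interference) and the continuous secondary outcomes with a baseline measurement (body weight, ActivPAL measures), the model contains the baseline value, intervention arm and sex as the stratification factor, regardless of observed balance. Any other covariate, such as age, is named before outcome data are examined or appears only in a labelled sensitivity analysis.

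Do not extend this to app use or retention. Neither has a baseline value: app use is marked only during the intervention in the assessments table, and retention is a count of completers ("We will record retention as the number of consented participants who complete baseline and follow-up testing"). Nor should it apply automatically to sparse non-continuous outcomes, where the plan allows another link function. Whether the roughly five run-in participants are analysed is a separate question that this sentence does not settle.

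The cost is one sentence and one degree of freedom, with no new data. If sex turns out not to be prognostic, the interval is about 0.2–0.4% wider with 30 complete cases and about 1.0% wider with 20% dropout.

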item)										
PROMIS Pain	Primary	X	X				X			
Interference Scale	*RCT Phase									
(8 item)										
Short Physical	Primary		X				X			
Performance	*RCT Phase									
Battery (SPPB)										
Mobility	Other		X				X			
Assessment Tool										
Short Form (MAT-										
SF)										
In-Home Weight	Other				X				X	
(Connected Scale)										
Sedentary Activity	Secondary		X				X			
& Transitions										
(ActivPal)										
Steps, Light and	Secondary			X		X				
Vigorous Activity						*only week				
(ActivPal)						12				
Sedentary Activity	Other	X			X				X	
& Transitions										
(Fitbit)										
Steps, Light and	Other	X			X				X	
Vigorous Activity										
(Fitbit)										
Daily Pain (EMA)	Other	X		X	X	X			X	
Daily Affect (EMA)	Other			X		X				
Medication used?	Other			X		X				
(EMA)										
App Use (count)	Secondary				X					
Retention	Secondary						X			
L			l .			1 1		1		1

Study Measure(s)

- 1. Baseline demographic data will be recorded based on participant self-report. Medical information on prior and existing co-morbidities and hospitalizations will be ascertained by self-report and confirmed by direct query of the participant at the screening visit. We will also record medication use by asking participants to bring in all medications (including nutritional supplements).
- 2. Adverse events will be assessed by asking participants at each assessment visit, and during weekly telecoaching calls. Participants will be asked to report any health changes, injuries, etc. and these will be recorded using the Adverse Event Form.
- 3. Physical function (a primary outcome of this study) will be assessed using the Short Physical Performance Battery (SPPB¹⁸), which is a measure of lower-extremity function consisting of walking speed, balance, and repeated chair stands. Perceptions of physical functioning will be assessed using the Mobility Assessment Tool Short Form (MAT-SF²⁹).
- 4. Pain (the second primary outcome of this study) will be assessed using the PROMIS¹⁷ pain intensity (3 item) and pain interference (8 item) scales.
- 5. Body weight: Body weight will be measured in-clinic on the same scale. As a process measure, we will also obtain body weights weekly from individuals in-home using a connected scale.

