Informed Consent: The informed consent process will follow the procedures of the WFSM Institutional Review Board. The potential participant is mailed the informed consent form and asked to read it before their initial visit. The form is written in simple, easy-to-understand language. At first contact with the prospective participant during the initial visit, the study staff member will explain the purpose, methods and extent of the study. We require study staff to review all of the key aspects of the study verbally with the potential participants and to question potential participants to ascertain whether s/he has understood the information. Potential participants are encouraged to ask questions regarding the consent form and the study. A copy of the signed and dated consent form will be given to participants, and the original document will be placed in their individual study file, which will be stored in a secure location. In compliance with the Health Insurance Portability and Accountability Act (HIPAA) and the Standards for Privacy of Individually Identifiable Health Information of the Department of Health and Human Services, we will access personal health information only after obtaining informed consent.

Potential Study Risks: There are inherent potential risks to human subjects who participate in any research study and the potential risks to study participants in this study are listed below. Any injuries or illnesses (adverse events) during the course of a participant's enrollment in the study are monitored regularly.

- Physical function tests: There is a small risk of injury during the physical function tests, such as muscle strains or pulls, falls, or joint injury. Risks will be minimized by having experienced/trained staff conducting these assessments. A warm-up and range of motion practice will be conducted before testing. If a participant reports pain, dizziness, or other medical problem, the test will be terminated.
- Weight loss at any age include the concomitant loss of lean (muscle and bone) tissue along with fat mass loss. However, the clinical impact of this muscle and bone loss is not known. Since most adults with obesity have a higher muscle mass and bone density, this risk is mitigated by excluding individuals who are non-obese and less likely to benefit from weight loss.

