 - During the behavioral weight loss classes, we will also provide nutrition education regarding adequate intake of calcium and Vitamin D, including encouraging use of dietary supplements. Participants will be counseled to consume, either using food or dietary supplements, at least 1300 mg of calcium and 1000 IU of Vitamin D daily.
- Risks of the movement intervention are minimal, but also may include an enhanced fall risk. This will be minimized by reviewing environmental factors that are known to increase fall risk.
- Risks associated with wearing the activity monitors are minimal, but may include minor skin irritations. Participants will be instructed to note these on their log and if it becomes bothersome to remove the device and call staff for further instructions.

Confidentiality and Privacy

Confidentiality will be protected by collecting only information needed to assess study outcomes, minimizing to the fullest extent possible the collection of any information that could directly identify study participants, and maintaining all study information in a secure manner. To help ensure subject privacy and confidentiality, only a unique study identifier will appear on the data collection form. Any collected patient identifying information corresponding to the unique study identifier will be maintained

on a separate master log. The master log will be kept secure, with access limited to designated study personnel. Following data collection, subject identifying information will be destroyed at the earliest opportunity, consistent with data validation and study design, producing an anonymous analytical data set. An entirely separate identifier number will be used for any data collected via the web, and the key stored offline in a secure location. Data access will be limited to study staff. Data and records will be kept locked and secured, with any computer data password protected. No reference to any individual participant will appear in reports, presentations, or publications that may arise from the study.

Data and Safety Monitoring

The co-PIs, along with the study physician, will be responsible for the overall monitoring of the data and safety of study participants. In addition, we will use the WFU Pepper Center's appointed Data Safety Monitoring Board. This board meets twice a year and reviews all studies that are supported by the WFU Pepper Center. A copy of the report will be reported to the IRB after each meeting.

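### Falls are the named risk of the movement intervention, but nothing in on-study adverse-event collection assures that falls without injury are captured

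*Combined protocol and SAP*

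**What the plan says.** **The risk.** Under Potential Study Risks, the movement intervention's risks "are minimal, but also may include an enhanced fall risk". The stated mitigation is: "This will be minimized by reviewing environmental factors that are known to increase fall risk". No recording step is attached to it.

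**Entry.** The functional-status row of the eligibility table excludes anyone with ">1 fall (injurious or non-injurious) in past year". It makes an exception for an uninjured fall in which the person was pushed or pulled by something else. The recruitment text gives fall-risk reduction as the reason for excluding repeat fallers.

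**On study.** The introduction to Potential Study Risks says that "Any injuries or illnesses (adverse events) during the course of" enrolment are monitored regularly. Study Measure(s), item 2, says adverse events "will be assessed by asking participants at each assessment visit, and during weekly telecoaching calls". It continues: "Participants will be asked to report any health changes, injuries, etc. and these will be recorded using the Adverse Event Form". The reporting section has minor events recorded and reported within seven days, with a description, date and location for each event.

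**Not found.** The measures list has no fall item. The assessment table has a single adverse-events row that itemises no event type. Statistical Analyses plans no fall or adverse-event summary.

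**The concern.** The eligibility table shows that the authors regard a fall as relevant to safety whether or not it hurts anyone, and it supplies a workable definition. That definition is not carried into on-study collection. A participant who loses balance at home, goes down and gets up unhurt has had neither an injury nor, in ordinary speech, a change in health. The prompt as described gives that person no particular reason to mention it.

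Falls are the only harm the documents attribute to the movement component, and the pilot is meant to inform a larger trial. If unhurt falls are recorded only when volunteered, the count passed to the monitoring board mixes true frequency with willingness to mention it. A fall that was never asked about cannot be recovered at analysis.

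**Working it through.** The documents give no fall rate, expected fall count or safety sample-size calculation, so there is no stated figure to reproduce. The check is mainly textual, followed by arithmetic on labelled assumptions.

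**1. Is a fall without injury covered?**

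| Place | What counts | Unhurt fall covered? |
|---|---|---|
| Eligibility table | Falls with or without injury, with one exception | Yes, explicitly |
| Potential Study Risks, introduction | Injuries or illnesses | Not on its face |
| Study Measure(s), item 2 | Health changes, injuries, and an open remainder | Possibly, if volunteered |
| Potential Study Risks, function tests | Falls named among examples of injury: "such as muscle strains or pulls, falls, or joint injury" | Unclear; concerns supervised testing |
| Assessment table | Adverse events, one row | Not specified |

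No place excludes unhurt falls from recording, and none requires that they be asked about.

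**2. Is the prompt the same in both arms?** Weekly questioning is tied to telecoaching calls, which the intervention arm receives. Under Phase II, the wait-list arm gets monthly calls for engagement, with no adverse-event question stated. Up to the week-12 comparison, P2V4 is the only post-baseline point at which the documents clearly have both arms asked.

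**3. How large is the loss?** Let *s* be the share of falls that cause injury (taken as always recorded) and *v* the share of unhurt falls volunteered under the open prompt. Then

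share lost = (1 − *s*)(1 − *v*).

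Neither quantity is in the documents. Assume *s* from 10% to 50%:
- *v* = 0: from (1 − 0.5) = 50% to (1 − 0.1) = 90% lost.
- *v* = 1: 0% lost.

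In counts, assume 15 per arm and 0.3 to 1.0 falls per person-year. Follow-up is 15 × 12/52 = 3.46 person-years per arm, giving 3.46 × 0.3 = 1.04 to 3.46 × 1.0 = 3.46 expected falls. The number lost then runs from 0 to 3.46 × 0.9 = 3.1 per arm. Every input except the 12 weeks is an assumption, so this range shows only that the loss is undetermined.

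**4. What would full capture give?** Solving (1 − *p*)^n = 0.025 gives the upper limit of a two-sided 95% interval when no one falls: *p* = 1 − 0.025^(1/n).
- n = 15: 21.8% (one-sided 95%, using 0.05: 18.1%).
- n = 12: 26.5% (one-sided 22.1%). This is roughly the arm size if the trial run of about 5 people, all given the intervention, counts within the 30: (30 − 5)/2 = 12.5.

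For a between-arm test at two-sided 0.05,

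power = Φ{[√n·|p₂ − p₁| − 1.96·√(2p̄(1 − p̄))] / √(p₁(1 − p₁) + p₂(1 − p₂))}.

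With n = 15 and assumed risks of 10% and 20%: (0.387 − 0.990)/0.500 = −1.205, so power is 11%, or 4% by Fisher's exact test. For 10% against 30% the figures are 27% and 15%. About 199 per arm would be needed for 80% power at 10% against 20%.

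**The case against.** The strongest reply is that the text does not restrict adverse events to injuries. The phrase about injuries and illnesses is a parenthesis in a risk narrative, not a formal definition. The operative rule is item 2, whose open-ended wording can take in an unhurt fall. The function-test bullet places falls among injuries. The Adverse Event Form is not reproduced, so it may already carry a fall prompt. Minor events are to be recorded with description, date and location. An eligibility screen and an on-study prompt serve different purposes and need not share wording.

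Much of this stands, and it rules out several stronger readings:
- A reader might infer that unhurt falls will go unrecorded. No text says so, and the open prompt could catch some.
- A reader might infer that the fall risk cannot be judged at all because of this wording. Falls that injure would be recorded, and the sample size limits any between-arm judgement even with complete capture.
- A reader might infer that most falls would be missed. That figure merely restates an assumed injury share and supposes that nobody volunteers an unhurt fall.
- A reader might infer that someone passing the entry fall limit during the program would breach a rule. The documents set no on-study fall limit.

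What the reply does not meet is the lack of assurance. An open remainder depends on the participant mentioning the fall and on staff choosing to record it. The function-test bullet concerns supervised testing, not home activity. Low power is no reason to leave the event unasked, since a descriptive count is what a pilot of this size can supply.

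**Conclusion.** The point holds as a gap in ascertainment. The protocol names an enhanced fall risk and counts falls with or without injury at entry, but specifies no fall question, definition or summary on study. Capture of falls without injury is therefore not assured, and the documented contact schedule could make it differ by arm. Falls cannot be reliably counted or described by arm as the plan stands.

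The size of the loss cannot be derived from the documents. The 0 to 90% range rests on an assumed injury share and an unknown rate of volunteering. The conclusion also assumes that the unseen Adverse Event Form has no fall item; if it has one, what remains is to state it in the protocol and align the recall period. This is an inexpensive improvement to safety data and does not affect the primary-outcome analysis.

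**What to change.** Add one scripted question to the Adverse Event Form: *Have you fallen, with or without injury, since we last asked?* Use the eligibility table's definition, including its exception for uninjured falls caused by being pushed or pulled. Record the date, the activity at the time, whether the fall occurred during a program activity, and whether there was injury.

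Ask it on the calls already made to each arm: the weekly telecoaching calls and the monthly wait-list calls. At P2V4, ask both arms the same question with the same recall period, since baseline, and base the between-arm table on that answer. The table then does not depend on weekly against monthly questioning. Keep call-based reports as supporting detail.

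Report to the monitoring board, by arm, the number of people who fell and the number of falls, with and without injury. Make it descriptive, with no between-arm test. List the non-randomised trial-run participants separately.

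The cost is one question, a few form fields and slightly more minor events to record and review. Recall since baseline will miss some falls, which is the price of a common basis; the call records give a partial check.
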